3.4. Enrollment Strategy

Study subjects will be recruited from the Institution/clinical site's subject database and/or utilizing Independent Ethics Committee (IEC) or Institutional Review Board (IRB) approved materials.

4. STUDY DESIGN AND RATIONALE

4.1. Description of Study Design

This will be a 4-visit, randomized, controlled, single-masked, bilateral wear, dispensing, 2-treatment, 2-sequence, 2-period crossover study.

At the initial visit (Visit 1), eligible subjects will be randomized into one of two unique sequences to wear two different study lenses one at a time over two wear periods (test/control or control/test). Subjects will wear each study lens type in a daily wear, daily disposable modality for approximately 1-week. Subjects will be advised to wear the study lenses for a minimum of 8 hours per day for at least 5 days during each wear period. Subjective comfort, vision and handling will be assessed using the CLUE questionnaire at both fitting and follow-up visits for each wear period. Monocular HLHC VA will be assessed at the follow-up evaluation using ETDRS charts. There will be a washout period of 7 ± 2 days duration between wear periods. Subjects will not have access to the study lenses following completion of the protocol.

Unscheduled visits may be conducted, if appropriate, and lost or damaged lenses may be replaced when necessary.

4.2. Study Design Rationale

The primary objective of this study is to evaluate the clinical performance of the test lenses against predefined targets specified in the Customer Requirements Document, based on historical performance of the ACUVUE® OASYS 1-Day for Astigmatism contact lenses.⁶ While the co-primary, safety, efficacy and secondary hypotheses will be tested for the test lenses only, a two-treatment by two-period crossover design was chosen for this study. This was considered the optimal design as it will address the primary, secondary and exploratory objectives as well as provide clinical data for the control lens. The rationale for collecting data on a marketed product is to monitor the clinical performance, as the lenses for this study will be manufactured from the Flexible Manufacturing Platform (FMP), which is not the distributional line utilized for the Control lens (AO1Dfa). Moreover, this is only the second study where lenses from the FMP line are being evaluated.

Clinical Study Protocol
Johnson & Johnson Vision Care, Inc.

Though the primary hypothesis is to test only the investigational study lens, the study design is not anticipated to have an impact on subjects' visual acuity, toric lens orientation, rotational stability, lens fit or SLFs since these endpoints are objective in nature, there will be a 1-week washout period between study lenses, and different EDTRS charts will be utilized for each eye (left vs. right) to help reduce potential for optotype memorization during collection of visual acuity.

However, there is a potential risk of carryover effect in all data collected from this study design, however, this is a greater risk for subjective responses than objective ones, i.e., CLUE vision scores. If a sequence effect is observed in the statistical model, then the primary hypothesis will be tested on data from the first period only.

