2.3. Hypotheses

Co-Primary Safety Hypotheses:

1. The percentage of eyes with one or more clinically significant, study-lens related, slit-lamp findings (Grade 3 or 4) following wear of the test lenses will be less than 5%.
2. At least 80% of lens fits will be acceptable at the dispensing visit.

Both co-primary *safety* hypotheses must be met in order to test any co-primary *efficacy* hypotheses.

Co-Primary Efficacy Hypotheses:

1. After approximately 1-week of wear, the mean monocular, high-luminance, high-contrast distance visual acuity for the test lens will be lower than 0.00 logMAR (equivalent to 20/20 Snellen visual acuity).
2. Following lens settling (at least 15 minutes) at the dispensing visit, at least 80% of lens fits will have absolute rotation less than or equal to 10 degrees.
3. Following lens settling (at least 15 minutes) at the dispensing visit, at least 80% of lens fits will have lens rotational stability with blink less than or equal to 5 degrees.
4. After approximately 1 week of wear, the mean overall CLUE™ Vision score for the test lens will be statistically greater than 62 points.

All safety and efficacy co-primary hypotheses must be satisfied in order to meet the study objectives and to test any secondary hypotheses.

Secondary Hypotheses:

1. After approximately 1 week of wear, the mean overall CLUE™ Handling score for the test lens will be greater than 61 points with 95% statistical confidence.
2. After approximately 1 week of wear, the mean overall CLUE™ Comfort score for the test lens will be greater than 58 points with 95% statistical confidence.

Clinical Study Protocol
Johnson & Johnson Vision Care, Inc.

Exploratory Hypotheses:

1. After approximately 1 week of wear, the test lens will be non-inferior to the control lens with respect to at least one of the following subjective questionnaire items asked at the follow-up visit:
 - a. Ability to see comfortably while driving during the day
 - b. My vision was clear enough to allow me to drive at night
 - c. Reduction in the feeling of tired eyes from using a computer or other digital device

A non-inferiority margin of 10% will be used.

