14. STATISTICAL METHODS

14.1. General Considerations

Statistical Analysis will be undertaken by the sponsor or under the authority of the sponsor. A general description of the statistical methods to be implemented in this clinical trial is outlined below. More details will be included in the stand-alone Statistical Analysis Plan (SAP). The SAP will be developed and finalized prior to database lock.

All data summaries and statistical analyses will be performed using the SAS software Version 9.4 SAS Institute, Cary, NC⁷. Throughout the analysis of data, the results for each subject/eye will be used when available for summarization and statistical analysis. For the analysis of co-primary safety endpoints, unscheduled visits will be summarized separately and will not be excluded from the statistical analysis. However, for the analysis of co-primary efficacy endpoints and secondary endpoints, unscheduled visits will be summarized separately and excluded from the statistical analysis.

Summary tables (descriptive statistics and/or frequency tables) will be provided for all baseline variables, efficacy variables and safety variables as appropriate. Continuous variables will be summarized with descriptive statistics

Clinical Study Protocol
Johnson & Johnson Vision Care, Inc.

(n, mean, standard deviation(SD), median, minimum and maximum). Frequency count and percentage of subject.s or eyes within each catego1y will be provided for categorical data.

Summaries will be presented by separately for each time point (baseline, fitting and 1-week follow-up) and will be perfo1med separately by completion status (Safety Population, Per-Protocol Population or Intent-to-treat, when appropriate).

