14.2. Sample Size Justification

This study was designed and powered to test for superiority of the test lens after 1-week of lens wear with respect to the following: distance monocular HLHC visual acuity (logMAR), subjective vision scores, toric lens orientation, and rotational stability. This study was also powered to test superiority of the test lenses with respect to grade 3 or higher slit lamp findings and percentage of eyes with acceptable lens fit. Additionally, this study was also powered to test for superiority with respect to CLUE Comfort and Handling scores after 1-week of lens wear. The described alpha adjustment is also factored into these estimations of sample size and power.

The sample size for co-prima1y efficacy endpoints was estimated to achieve a minimum statistical power of 90% for distance monocular visual acuity (logMAR), toric lens orientation, rotational stability, and CLUE Vision scores using a 2-sided type I eITor rate of 5%. Co-prima1y safety endpoints (grade 3 or higher SLFs and acceptable lens fitting) were estimated to achieve a minimum statistical power of 99% with 95% central posterior credible interval.

A summa1y of historical studies utilized in the sample size calculation are summarized in Table 7 below, while Table 8 summarizes the historical data for the test lens by endpoint.

Table 7: Historical Studies Utilized for Sample Size Calculations

Study Number	Design	Sample Size	Number in Safety	Number in PP
4	2x3	Feasibility	145	144
	2x3	Conformation	126	26

PP: Per-Protocol

Table 8: Historical Data by Endpoint - Test Lens

Endpoint Type	Endpoint	Data Type	Value
*Primary Safety	Grade 3 + SLFs (Adverse Event)	Rate	0%
	Acceptable Lens Fitting		100%
**Primaiy Efficacy	Distance Monocular Visual Acuity (logMAR)	Mean (SD)	-0.115 (0.0769)
	Absolute Toric Rotation 10°		97.5%
	Lens Stability with Blinks 5°		100%
	CLUE Vision Scores		67.4 (19.67)
**Secondary	CLUE Handling Scores	Mean (SD)	65.4 (21.50)
	CLUE Comfort Scores		67.9 (21.50)

SD=Standard Deviation

*Summaries for the primaiy safety endpoints were provided for the safety population; all available data was included

**Summaries for primary efficacy and seconda1y endpoints were provided for the per-protocol population at the 1-week follow-up evaluation.

Clinical Study Protocol

CR-6521, v 3.0

■ JJV C CONFIDENTIAL

**Clinical Study Protocol
Johnson & Johnson Vision Care, Inc.**

Co-Primary Safety Endpoint Sample Size Calculations:

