14.5. Primary Analysis

Methodology regarding the plan for testing and/or handling statistical associations between co-primary safety and/or efficacy endpoints will be documented in the SAP.

Co-Primary Safety Analyses:

All primary safety analysis will be conducted on the safety population.

Grade 3 or Higher SLF

Grade 3 of Higher SLFs will be analyzed using a Bayesian beta-binomial model with correlated binary data.⁸

The Model:

Let \mathbb{Y}_1 and \mathbb{Y}_2 denote the binary outcomes of lens fit acceptance (Yes/No) in left and right eyes, respectively, across dispensing and follow-up visits when wearing the test lens. Considering the correlation, $\rho\rho$, between \mathbb{Y}_1 and \mathbb{Y}_2 , the distribution of the sum $YY = \mathbb{Y}_1 + \mathbb{Y}_2$ is obtained by the mixture of two variables. One of them follow a binomial distribution $BB\BBB(2, \rho\rho)$ with mixing probability $(1 - \rho\rho)$ and the other one follows a modified Bernoulli distribution, $MMBB\BBB(1 - \rho\rho)$, taking value 0 and 2 rather than conventional 0 and 1, with mixing probability $\rho\rho$:

$$PP(YY = yy | \rho\rho, \rho\rho) = (1 - \rho\rho)BB\BBB(2, \rho\rho)I_{AA1} + \rho\rho MMBB\BBB(1 - \rho\rho)I_{AA2},$$

where $I_{AA1} = \{0, 1, 2\}$, $I_{AA2} = \{0, 2\}$ and $\rho\rho$ is the probability of success (i.e., acceptable lens fitting).

To overcome the complexity of the mixture likelihood a latent variable ZZ_{ii} , $i = 1, 2$ is introduced in the model to indicate in which component of the model the observation yy_{ii} , $i=1, 2$, belongs to, that is,

$$ZZ = \begin{cases} 1, & \text{if the observation belong to the MBern}(p), \\ 0, & \text{if the observation belong to the Bin}(2, p) \end{cases}$$

The joint distribution of the augmented data (YY_{ii}, ZZ_{ii}) , $BB = 1, 2$, is given by

$$P(Y = y, Z = z | p, \rho) = \rho^{z_i} p^{y_i z_i / 2} (1 - p)^{(2 - y_i) z_i / 2} (1 - \rho)^{1 - z_i} \prod_{i=1}^2 p_{y_i}^{y_i(1 - z_i)} (1 - p)^{(2 - y_i)(1 - z_i)}$$

The probability p links to the regression variables through a logit transformation as follow:

$$\text{logit}(p) = \beta_0 + \beta_1 \text{lens}$$

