$$\begin{aligned} H_{H_0}: pp_{TTTTTTTT} &\leq 80\% \\ H_{H_A}: pp_{TTTTTTTT} &> 80\% \end{aligned}$$

Where $pp_{TTTTTTTT}$, represents the population percentage for the percentage of eyes wearing the test lens with lens stability with blinks $\leq 5^\circ$. Superiority will be declared if the lower limit of the 95% CI is above 80.

CLUE Vision Scores

CLUE vision scores after 1 week of lens wear will be analyzed using a linear mixed model adjusting for baseline scores as a covariate. Sequence of lens wear, lens type and period will be included in the model as fixed effects. Subject characteristics such as, gender, age and/or cylinder power may be included in the model if appropriate. Site ID will be included in the model as a random effect (G-side). The residual error between measurements within the same subject will be modeled using an unstructured (UN) covariance structure. If the model fails to converge with a UN covariance, then a compound systemic (CS) covariance structure will be used. The Kenward and Roger Method will be used for the denominator degrees of freedom.¹¹ CLUE Vision Scores estimates for each study lens will be estimated using 95% confidence intervals (CI) constructed for the least-square means (LSM).

Clinical Study Protocol
Johnson & Johnson Vision Care, Inc.

Primary Efficacy Hypothesis 4:

The null and alternative hypothesis to test for superiority of CLUE vision score for the test lens relative to the threshold 62 are as follows:

$$\begin{aligned} H_0: \mu_{TTTTTTTT} &\leq 62 \\ H_A: \mu_{TTTTTTTT} &> 62 \end{aligned}$$

Where $\mu_{TTTTTTTT}$, represents the population mean for test lens after 1 week of lens wear with respect to CLUE vision scores. Superiority will be declared if the lower limit of the 95% CI is above 62.

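### Section 4.2 moves the primary test to period 1 data on an undefined sequence effect; section 14 does not carry the switch, and the period 1 test is correlated with its own trigger

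*Combined protocol and SAP*

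**What the plan says.** Section 4.2 accepts that carryover could affect all data but adds that "this is a greater risk for subjective responses than objective ones, i.e., CLUE vision scores". It expects no effect of the design on visual acuity, orientation, stability, fit or slit lamp findings. It then sets a rule: "If a sequence effect is observed in the statistical model, then the primary hypothesis will be tested on data from the first period only".

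Section 2.3 has six co-primary hypotheses, two for safety and four for efficacy, and "All safety and efficacy co-primary hypotheses must be satisfied in order to meet the study objectives".

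In section 14.5 each of the four efficacy models carries the same statement: "Sequence of lens wear, lens type and period will be included in the model as fixed effects". The safety model has lens as its only regression term. For CLUE Vision, "Superiority will be declared if the lower limit of the 95% CI is above 62". None of 14.2, 14.4 and 14.5 mentions a test of sequence, a move to period 1 or a model for period 1. Section 14.1 leaves further detail to a stand-alone SAP that is not among the supplied documents.

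Tables 8 and 9 give CLUE Vision a mean of 67.4 (SD 19.67) and 91% power with 144 subjects. Section 14.2 puts combined power at about 86%. Section 4.3 targets at least 165 completers.

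**The concern.** The sentence in 4.2 is a decision rule: it changes the data on which a primary hypothesis is tested. It speaks of one primary hypothesis where there are six, and it gives no criterion for deciding that a sequence effect is present. An estimated sequence effect is never exactly zero, so as written the choice is open once data are in hand.

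Two problems would remain even if a level were added. The efficacy models of 14.5 do not yield a test-lens mean from period 1 alone. And the subjects who supply the period 1 test-lens mean are half of the comparison that triggers the switch, so a chance imbalance between the sequence groups both fires the rule and shifts the result that replaces the planned one. CLUE Vision is where this matters: it sets the sample size and has the least spare power.

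**Working it through.** **Inputs.** From the documents: CLUE Vision mean 67.4 and SD 19.67 (Table 8); threshold 62, so the difference is 5.4; 144 subjects (Table 9) and 165 (4.3); pass if the lower limit of the two-sided 95% CI exceeds 62, which is one-sided 2.5%. Assumed: equal sequence groups; within-subject correlation r of 0.3–0.7; a two-sided sequence t-test on subject sums at 5% or 10%; the same SD for both lenses; no baseline covariate, site effect or missing data.

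**1. The plan's own figure.** One-sample t-test power with noncentrality (5.4/19.67)×√n:
- n = 144: noncentrality 3.29, power 90.5% at one-sided 2.5%. This reproduces the stated 91%.
- n = 165: 93.9%.
- Combined, with the other five hypotheses at 99%: 0.99⁵ × 0.905 = 0.951 × 0.905 = 0.861, the stated 86%. At 165: 0.951 × 0.939 = 0.893.

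**2. Estimability.** With intercept, sequence, lens type and period, the design has rank 4 of 4 on both periods. On period 1, period is constant and sequence and lens type are the same split, so the rank is 2 of 4. The test-lens least-squares mean is then not estimable, and there is no covariance across periods to model. A model with lens type alone is estimable. The two safety models have lens only and are unaffected.

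**3. Correlation of trigger and fallback.** With h subjects per sequence and variance σ²:
- variance of the difference in mean subject sums: 4σ²(1+r)/h
- variance of the period 1 test-lens mean: σ²/h
- covariance: σ²(1+r)/h
- correlation: √(1+r)/2, which is 0.57 at r = 0.3 and 0.65 at r = 0.7

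For the two-period mean the contributions of the two groups cancel and the correlation is 0. The trigger level does not enter these formulas.

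**4. Size with no carryover** (simulation; ranges over r and trigger level):

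| CLUE Vision | Two-period test | With the switch |
|---|---|---|
| One-sided error at true mean 62 | 2.5% | 2.8–3.4% |
| Power at 67.4, n = 144 | 90.5% | 87–89% |
| Power at 67.4, n = 165 | 94% | 90–92% |
| Combined power, n = 144 | 86% | 83–85% |
| Combined power, n = 165 | 89% | 86–88% |
| Error in trials where the rule fires | 2–4% | 9–15% |
| Power in trials where the rule fires | 90–95% | about 51–60% |

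The 9–15% is an average of 18–29% when the test-first group scored higher and about 0% when it scored lower.

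**5. With carryover on period 2 test-lens scores.** The fixed rule passes if the two-period CI passes and the period 1 test-lens mean also exceeds 62.

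| Setting | Two-period only | Switch | Fixed rule |
|---|---|---|---|
| False passes, +5 points, n = 144 | 33% | 25–29% | 27–28% |
| False passes, +5 points, n = 165 | 37% | 27–32% | 30% |
| Power at 67.4, −5 points, n = 144 | 42% | 49–53% | 42% |

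With no carryover the fixed rule does not raise the error above 2.5%. Its power is 90.2–90.5% at 144 and 93.6–93.9% at 165.

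**6. Alpha in 14.2.** The general paragraph says two-sided 5%. The paragraph on visual acuity and CLUE Vision says one-sided 5%.
- CLUE Vision, n = 144: 90.5% at one-sided 2.5%, 94.9% at one-sided 5%. The stated 91% fits 2.5%.
- Visual acuity, n = 9, mean −0.115, SD 0.0769, noncentrality (0.115/0.0769)×√9 = 4.49: 97.4% at one-sided 2.5%, 99.2% at one-sided 5%. The stated 99% fits 5%.

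The two rows were therefore calculated at different levels.

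**The case against.** - **The SAP may define the rule.** It may, and the missing test, level and model could be supplied there. No section that defers to the SAP mentions this rule, though, and a level would not remove the correlation in step 3.
- **The rule guards against a risk that 4.2 names.** This stands. Under a favourable 5-point carryover the switch lets through fewer false passes than the two-period test alone, and under an unfavourable one it has higher power. A reader might infer that the sentence in 4.2 should simply be deleted. Deletion with nothing in its place would lose that protection, and nothing in the documents shows carryover to be unlikely enough to ignore.
- **The average effect is small.** Also true. At 165 completers CLUE Vision still meets the 90% minimum in 14.2, and all six hypotheses must pass. The calculation also omits the baseline adjustment in 14.5. With an assumed baseline correlation of 0.5 and r = 0.5, power with the switch is about 90–93% at 144 and 94–95% at 165, so a shortfall at 144 is not established for the specified model.
- **Software would drop the redundant terms, and a lens-only model is the natural reading.** That is reasonable, but it is a model the plan does not state.
- **Scope.** A reader might infer that chance switches on all four efficacy endpoints endanger the trial. They do not: Table 9 needs 9 subjects for visual acuity and 40 for orientation, the fallback leaves at least 72, and stability assumes a higher rate than orientation against the same 80%.

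**Conclusion.** The point holds as a defect in specification and in the choice of analysis, and it is worth correcting. The switch is undefined in 4.2 and absent from section 14, its efficacy model is not estimable on period 1 as specified, and its result depends on its own trigger. On average the harm to CLUE Vision is modest: about half a point of one-sided error, and roughly 1.5 to 4 points of power before baseline adjustment. In the 5–10% of trials where the rule would fire by chance, the outcome turns largely on which sequence group happened to score higher.

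Three stronger readings are not supported. The 9–15% is conditional on the rule firing and is not the trial's error rate. The 63% (n = 72) or 69% (n = 82) power of a period 1 test would apply only if that test were always used. And the estimability problem concerns the period 1 fallback for the efficacy models, not the two-period analysis or the safety models.

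The sizes rest on the assumed trigger level, r, equal groups and equal SDs. The estimability result needs none of these, and the correlation of trigger and fallback holds at any trigger level. That CLUE Vision is the intended endpoint is an inference from the sentence before the rule.

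**What to change.** Replace the conditional switch in 4.2 with a fixed rule in 14.5:
- Make the two-period mixed model the only primary analysis.
- To keep some protection against carryover, also require the period 1 test-lens CLUE Vision mean, from a model with lens type only, to exceed 62.
- Always report that period 1 estimate with its 95% CI as a pre-specified sensitivity analysis.

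This takes one sentence in 4.2 and one or two in 14.5, and no new data. It costs 0.1–0.3 points of power. Under favourable carryover it lets through 1–3 points more false passes than a switch triggered at 10%. Under unfavourable carryover it does not help, and the switch has higher power there.

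If the switch is kept, state the endpoint, the sequence test, its level and the period 1 model in 14.5, and restate the CLUE Vision and combined power with the rule included.

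Separately, reconcile the alpha in 14.2. State one-sided 2.5% for both visual acuity and CLUE Vision, to match the 95% CI rule, and restate the visual acuity row (n = 9) as about 97%. Its power at the planned sample size is essentially 100%, so nothing else changes.

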4.3. Enrollment Target and Study Duration

This study will have an enrollment target of approximately 180 subjects, with a target of at least 165 to complete. The study will be conducted at up to 14 clinical sites, where the enrollment target for each site will be approximately 10 to 20 subjects. A subject will be considered enrolled upon signing of the informed consent form.

At Visit 1, eligible subjects will be randomized to one of two lens wear sequences. There will be 4 visits in total per subject; total study duration including the enrollment period is expected to be approximately 10 weeks. Subjects who are discontinued prior to the final evaluation may be replaced at the discretion of the study sponsor. The investigation will end at the time that the study data is hard locked.

